#### 2.c Subject Recruitment Plans and Consent Process

Patients will be recruited from the pool of patients seen at Washington University/BJH dermatology clinics with existing and new diagnoses of lichen planopilaris and frontal fibrosing alopecia. Recruitment will be by word of mouth. Participants will be adequately informed about the study and have an opportunity to ask questions prior to enrollment. They will be seen during routine dermatology clinic visits and evaluated per protocol to determine eligibility for the study. Patients will have an opportunity to read and take home the consent form. Enrollment will be on a rolling basis between September 1st and October 31st, 2019. Patients who enroll in the study will be followed in [name] dermatology clinic at [name] (BJH West County). We will confirm with patients that they have decision-making capacity and the ability to understand the risks and benefits of the treatment.

Patients who do not respond to the invitation to participate in the study will be contacted at the phone number in their medical record to address any questions they may have and to confirm whether or not they will participate. Opt-out procedures include verbally indicating that they do not wish to participate.

Study participants will receive a copy of the consent document for their records. Participants will be given a signed copy of the consent document. This will be provided to them at the time of signing. The form will also be scanned into their electronic medical record.

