#### Background

Lichen planopilaris (LPP) is an inflammatory, cicatricial alopecia, of which frontal fibrosing alopecia is considered a clinical variant. Clinical features of LPP include perifollicular erythema and scaling leading to destruction of follicular ostia and patchy scarring alopecia. In the frontal fibrosing alopecia variant, hair loss occurs on the frontotermporal region, often with associated eyebrow loss. Symptoms include pruritus, burning, pain, and tenderness. Treatment options are limited and yield inconsistent results. High potency topical steroids and topical tacrolimus are recommended as first line therapies for primary cicatricial alopecias. However, topical corticosteroids may be less effective in FFA. Other frequently utilized treatments include intralesional triamcinolone acetonide and topical minoxidil. Hydroxychloroquine and doxycycline are often used as systemic treatments in both LPP and FFA, whereas finasteride/dutasteride have been reported successfully in FFA. Overall, the level of evidence for the above treatments is limited to level IV or V evidence, and further studies into this scarring disease are needed.

Oral naltrexone is FDA approved to treat opioid dependence and alcohol use disorder at doses from 50-100mg/day. At lower doses of 1-5mg/day, naltrexone has been used off-label with success in treatment of several dermatologic conditions including lichen planopilaris. A recent case series of four patients with lichen planopilaris and a subtype, frontal fibrosing alopecia, treated with oral low-dose naltrexone at 3mg daily showed reduction of pruritus, clinical evidence of scalp inflammation, and of disease progression.

While initial studies using LDN for dermatologic conditions is promising, the level of evidence is low, generally limited to case reports and series. Recently, three excellent summaries of evidence for naltrexone in dermatologic conditions have been published. A recent review article of therapy for FFA includes naltrexone at 3 mg/day in their FFA treatment algorithm.

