## E Study Design

#### E1 Overview or Design Summary

Uncontrolled open-label prospective study

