#### E2 Subject Selection and Withdrawal

#### 2.a Inclusion Criteria

Adults age 18 or greater with clinically or histologically confirmed diagnosis of lichen planopilaris or frontal fibrosing alopecia are eligible.

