#### 2.a Exclusion Criteria

Patients with known allergy or hypersensitivity to naltrexone will be excluded. Patients will be screened for opioid use with urine screen for opioids, and any patients with positive test or concurrent use of opioids will be excluded from the study. Postmarketing reports of suicidal thoughts, attempted suicide and depression have been reported with high dose naltrexone. While no reports of mood changes have been reported with low-dose naltrexone, patients will be counseled to report any mood changes that arise during

their treatment. Patients with currently active depression, schizophrenia, and bipolar disorder will be excluded.

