#### 3.f **Prior and Concomitant Therapy**

Low-dose naltrexone, 3mg orally to be taken daily, will be prescribed. They will be continued on their other treatment medications for lichen planopilaris (LPP) and frontal

fibrosing alopecia (FFA) during the study period without increasing dose. During the study period, other LPP and FFA medications may be decreased in dose or discontinued, but will not be increased or added. This will allow the investigators to analyze the specific benefit of naltrexone.

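### Nothing requires LPP/FFA therapy to be unchanged before month 0, so the response to a recently started therapy can enter the before-after contrasts and be read as naltrexone benefit

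*Combined protocol and SAP*

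**What the plan says.** All references are to the combined protocol and SAP.

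- **Recruitment (2.c)** takes patients "with existing and new diagnoses of lichen planopilaris and frontal fibrosing alopecia".
- **Inclusion (2.a)**: "Adults age 18 or greater with clinically or histologically confirmed diagnosis of lichen planopilaris or frontal fibrosing alopecia are eligible". No time since diagnosis and no period of stable background therapy is required.
- **Exclusion (2.a)** covers naltrexone hypersensitivity, opioid use and psychiatric illness ("Patients with currently active depression, schizophrenia, and bipolar disorder will be excluded"). It does not mention recently started LPP/FFA therapy.
- **Concomitant therapy (3.f)** continues other LPP/FFA treatment under this rule: "During the study period, other LPP and FFA medications may be decreased in dose or discontinued, but will not be increased or added". It then states the purpose: "This will allow the investigators to analyze the specific benefit of naltrexone".
- **Background (B1)** lists therapies that a newly diagnosed patient might be given, for example: "High potency topical steroids and topical tacrolimus are recommended as first line therapies for primary cicatricial alopecias". It also says that results with existing options are inconsistent.
- **Design (E1)**: "Uncontrolled open-label prospective study".
- **Analysis (G)** is a mixed model with a time effect and contrasts between time points among months 0, 3, 6 and 12. It names no term or subgroup for background therapy, its start date or time since diagnosis.

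**The concern.** The rule in section 3.f shows that the investigators see background therapy as a confounder of the before-after comparison. The rule works in one direction only: it stops therapy being added after month 0 but says nothing about therapy begun just before it. A patient given a first-line topical or a systemic drug days before month 0 meets every criterion and carries on with it at the same dose. If that therapy takes effect over the following months, the improvement falls between month 0 and the later visits.

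The problem is not confined to new diagnoses. An established patient whose treatment was stepped up just before month 0 raises it too.

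It also differs from the general lack of a control group. Natural course and regression to the mean cannot be separated out in this design. A recent therapy start is a dated event that can be recorded and handled in the analysis. What is at stake is whether a fall in itch, burning/pain, erythema or scale can be credited to naltrexone to the extent that section 3.f claims.

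**Working it through.** **Inputs from section G.** n = 75-100; two-sided α = 0.05; paired t-test; at least 80% power for 0.7-0.8 (0-10 scales) and 0.21-0.25 (0-3 scales); predicted falls of 2-3 and 1-2 points. The SDs are described only as a rule of thumb from the scale range. I take range/4: 10/4 = 2.5 and 3/4 = 0.75.

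**Step 1: reproduce the plan's figures.** Detectable difference = (1.960 + 0.842) × SD / √n.

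- 0-10 scales: 0.809 at n = 75 and 0.700 at n = 100 (exact t: 0.819 and 0.707).
- 0-3 scales: 0.243 and 0.210 (exact t: 0.246 and 0.212).

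These match the stated ranges. Exact power at the stated differences is 78.1% (n = 75, 0.8), 79.2% (100, 0.7), 81.3% (75, 0.25) and 79.2% (100, 0.21). Range/6 would give 0.47-0.55 and 0.14-0.16, which do not match. So 2.5 and 0.75 are the implied SDs.

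**Step 2: size of the artefact if naltrexone does nothing.** Let f be the share who recently started or stepped up other therapy, and d their mean improvement from it after month 0. Neither is in the documents; both are assumptions.

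- Bias in the mean change = f × d. A larger n does not reduce it.
- If only a share f improves, the change scores spread out: SD of change = √(SD² + f(1 − f)d²).
- Noncentrality = f × d × √n / SD of change. The chance of p<0.05 comes from the noncentral t with n − 1 degrees of freedom. The paired t-test stands in for the mixed-model contrast, as in the plan's own power calculation.

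Worked example, 0-10 scale, f = 0.3, d = 2: bias 0.6; SD = √(6.25 + 0.21 × 4) = 2.663. Noncentrality is 0.6 × 8.660 / 2.663 = 1.951 at n = 75 and 0.6 × 10 / 2.663 = 2.253 at n = 100. The chance of p<0.05 is 48.7% and 60.7%.

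| Scale | d | f | Bias f × d | Chance of p<0.05, n = 75 to 100 |
|---|---|---|---|---|
| 0-10 | 1 | 10% | 0.10 | 6.3-6.8% |
| 0-10 | 1 | 30% | 0.30 | 17.2-21.5% |
| 0-10 | 1 | 40% | 0.40 | 26.9-34.3% |
| 0-10 | 2 | 10% | 0.20 | 10.2-12.0% |
| 0-10 | 2 | 30% | 0.60 | 48.7-60.7% |
| 0-10 | 2 | 40% | 0.80 | 72.1-83.9% |
| 0-3 | 0.5 | 10% | 0.05 | 8.6-9.9% |
| 0-3 | 0.5 | 20% | 0.10 | 19.6-24.8% |
| 0-3 | 0.5 | 30% | 0.15 | 37.3-47.4% |
| 0-3 | 1 | 10% | 0.10 | 18.5-23.2% |
| 0-3 | 1 | 20% | 0.20 | 52.0-64.4% |
| 0-3 | 1 | 30% | 0.30 | 83.1-92.2% |

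**Step 3: compare with the plan's effects.** The largest bias in the table is 0.8 on the 0-10 scales and 0.3 on the 0-3 scales. Both are well short of the lowest predicted falls (2 and 1). They do reach the differences the study is powered to detect (0.7-0.8 and 0.21-0.25).

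**Step 4: what an analysis of the unchanged-therapy subset would cost.** The detectable difference at 80% power (exact t), with the larger n first, is:

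- 10% set aside (n = 90 or 68): 0.75-0.86 and 0.22-0.26.
- 30% set aside (n = 70 or 52): 0.85-0.99 and 0.26-0.30.
- 50% set aside (n = 50 or 38): 1.01-1.17 and 0.30-0.35.

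Power for falls of 2 points and 1 point stays above 99% throughout.

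**The case against.** The strongest reply is that the size is guesswork. Section 2.c allows new diagnoses but does not say they will be common, or that they will have started another therapy just before month 0. At 75-100 patients, f = 40% means 30-40 recent starters. The higher values of d (2 and 1) equal the low end of naltrexone's own predicted effect, whereas B1 describes existing treatments as inconsistent, with evidence no better than level IV or V. This stands, and it is why the table also shows d = 1 and d = 0.5 and why no single figure is offered.

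A reader might infer that the bias always favours the hypothesis. The documents do not support that. A recent therapy that does not work adds nothing, and one that had its full effect before month 0 is already in the baseline. The reductions and stops allowed by section 3.f push the other way, although nothing makes the two cancel.

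A reader might also infer that a positive result would be an artefact, or that the main analysis should be confined to patients stable for three months. Neither follows. The likely artefact is smaller than the predicted effects, and three months is a visit interval: the documents give no onset time for the other therapies.

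Finally, the data collection sheet named in L1 is not shown and may already capture therapy dates. If so, section G still gives no rule for using them.

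**Conclusion.** The gap is real. Followed as written, the plan admits patients with recently started or increased LPP/FFA therapy and has no means of separating their response to it from naltrexone's. It nevertheless says that its concomitant-therapy rule isolates naltrexone's benefit.

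The bias is f × d, usually towards the hypothesis if the recent therapy works. Its actual size cannot be known from the documents. Over the assumed ranges (f = 10-40%, d = 1-2 on the 0-10 scales; f = 10-30%, d = 0.5-1 on the 0-3 scales), the chance of a significant fall with an inert drug runs from barely above the nominal 5% to over 80-90%. These figures rest on the range/4 SDs, the mixture variance and the paired t approximation. The point merits a change to the plan, but it does not invalidate the study. Even with the change, the study remains uncontrolled and cannot exclude natural course or regression to the mean.

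**What to change.** 1. At month 0, record from the medical record the start date and last change of each LPP/FFA therapy, if the data collection sheet does not already do so.
2. In section G, pre-specify a sensitivity analysis that repeats the before-after contrasts in patients whose LPP/FFA therapy was unchanged for a stated period before month 0. The investigators should set the length; the plan's three-month visit interval is one option. Report recent starters separately.
3. In section 3.f, limit the attribution sentence to what an uncontrolled study can show.

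The all-patient analysis stays as planned, no patient is excluded and no one's care changes. The cost is a few extra data fields, one added analysis and lower precision in the subset.

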#### 2.d Randomization Method and Blinding

N/A, not randomized

#### 2.e Risks and Benefits

Based on case reports, we expect the participant to benefit though decrease in their symptoms (burning, itching) as well as decreased redness and scale and possibly slowing or halting disease progression.

This increased data would benefit society by providing further evidence for the use of low-dose naltrexone in lichen planopilaris and frontal fibrosing alopecia.

Use of naltrexone in patients on long-term opioids may induce opioid withdrawal, so patients will be screened for opioid use. Additionally, as LDN upregulates the number of opioid receptors, patients must be cautioned that this can potentiate the effect of opioid agonists, leading to risk of opioid overdose. Patients will be advised that if they require emergent pain control for other conditions, opioid alternatives should be considered or if

opioids are required, they are administered under the direct supervision of a physician. While long-term safety data are not available, side effects with low-dose naltrexone are minimal, not significantly different from placebo, and include vivid dreams, nightmares, and headaches. Morning dosing of low-dose naltrexone can decrease these effects, if present. Based on studies involving retrospective chart reviews of patients treated with LDN for multiple sclerosis and Crohn's disease without significant laboratory abnormality, Lee and Elston concluded that no laboratory testing is required in the absence of specific signs or symptoms. Postmarketing reports of suicidal thoughts, attempted suicide and depression have been reported with high dose naltrexone. While no reports of mood changes have been reported with low-dose naltrexone, patients will be counseled to report any mood changes that arise during their treatment.

#### 2.f Early Withdrawal of Subjects

Subjects may withdraw by telling the study team they are no longer interested in participating in the study or by sending a withdrawl letter. The investigator may also decide to end participation due to patient becoming ineligeable (see eligibility criteria above) or due to unforeseen safety issues.

#### 2.g When and How to Withdraw Subjects

Subjects will be contacted be phone or in person at a routine office visit.

#### 2.h Data Collection and Follow-up for Withdrawn Subjects

All data obtained prior to withdrawal will be included in the data analysis.

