## A Introduction

#### A1 Study Abstract

Oral naltrexone was initially FDA approved to treat opioid use disorder and alcohol dependence at doses from 50-100mg/day. At lower doses of 1-5mg/day, naltrexone has been used off-label with success in treatment of several dermatologic conditions including the scarring alopecia (irreversible hair loss), lichen planopilaris. A recent case series of four patients with lichen planopilaris and a subtype, frontal fibrosing alopecia, treated with oral low-dose naltrexone at 3mg daily showed reduction of itch, clinical evidence of inflammation of the scalp, and of disease progression. There were no reported adverse events.

Based on the promising evidence, we propose using low-dose naltrexone at a daily dose of 3mg to treat lichen planopilaris and frontal fibrosing alopecia. The patients would be continued on their other medications for these conditions. The study would be openlabel, so all participants would receive the low-dose naltrexone. Patients would be seen at monthly intervals over a period of six months to monitor their progress.

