#### 2.b Ethical Considerations

Eligeable subjects may take naltrexone without enrolling in the study to eliminate coercion.

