### F2 Schedule of Measurements

Performed at 0,3,6, and 12 month office visits.

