# G Statistical Plan

Longitudinal data from time points at 0,3,6 and 12 months will be analyzed for each component of the data collection form, including components of the patient assessment of itch and burning/pain (each on a 0-10 point scale), physician assessment for erythema and scale (each on a 0-3 scale) as well as longitudinal comparisons of measurement of the scalp involvement (distance in cm from the glabella to hairline in FFA, and area of scarring/redness/scaling in cm2 for LPP). See below for data collection form.

We predict that oral low-dose naltrexone would lead to approximately 2-3 point decrease in each of the 0-10 point patient assessments (itch and burning/pain) and a 1-2 point decrease in each of the 0-3 point physician assessments (erythema and scale). We expect the areas of scalp involvement to remain stable over the analysis period.

Patient characteristics will be summarized using descriptive statistics. The longitudinal outcomes will be analyzed using mixed model analysis to account for the correlation of measures from the same subject. Time effect will be assessed and contrasts will be used to compare mean difference between any two time points of interest. All statistical tests will be two-sided with a significance level of 0.05 and performed with SAS 9.4. Careful attention will be paid to ensuring that data satisfy assumptions required of a particular analytic strategy. When required assumptions are violated, we will explore the use of data transformations and potentially, perform some analyses using non-parametric or semi-parametric methods based on the rank of some variables.

Data on the quantitative effect size of naltrexone for LPP/FFA is limited, but based on clinical experience and descriptive case studies, we would expect patients to start at a 4-5/10 on the itch/pain/burning scales, and predict that it could decrease to 1-2/10 with

naltrexone treatment. Similarly, we expect that patients would start at a 1-2/3 on the physician assessments (erythema and scale) and predict that the physician assessments of erythema and scale could decrease to a 0-1/3. Finally, we expect the areas of scalp involvement to remain stable over the analysis period. Based on existing data showing low number of mild side effects and no serious adverse events, we plan to enroll 75-100 patients, which is the maximum number that we would expect to see over the study period given the low prevalence of disease.

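### Section 2.h provides for no exit score, so worsening that goes unscored before a patient leaves can bias the single-arm time effect towards benefit

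*Combined protocol and SAP*

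**What the plan says.** - **Treatment rule (E3, 3.f).** During the study, "other LPP and FFA medications may be decreased in dose or discontinued, but will not be increased or added".
- **Leaving (E2, 2.f and 2.g).** Subjects may leave when no longer interested. In addition, "The investigator may also decide to end participation due to patient becoming ineligeable", or may do so for unforeseen safety issues. Worsening is not named as a reason. On the mechanics, "Subjects will be contacted be phone or in person at a routine office visit".
- **Data from leavers (E2, 2.h).** The whole section is one sentence: "All data obtained prior to withdrawal will be included in the data analysis". It mentions no exit assessment, reason for leaving or later follow-up, although its title covers follow-up.
- **Access outside the study (E2, 2.b).** "Eligeable subjects may take naltrexone without enrolling in the study to eliminate coercion".
- **Scoring times.** F2 says "Performed at 0,3,6, and 12 month office visits", and 3.e and Section G use the same times. The abstract (A1) differs: "Patients would be seen at monthly intervals over a period of six months to monitor their progress".
- **Analysis (G).** "The longitudinal outcomes will be analyzed using mixed model analysis to account for the correlation of measures from the same subject". The section states no missing-data assumption, dropout allowance or sensitivity analysis.
- **Design (E1).** Uncontrolled and open-label.

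**The concern.** A patient who worsens and wants more LPP/FFA treatment cannot have it within 3.f. Leaving costs such a patient little, because 2.b makes naltrexone available outside the study. If the patient leaves between visits, the last score on file predates the worsening, and nothing in the plan asks for another.

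A likelihood-based mixed model copes with dropout that depends on scores already recorded. It does not cope with dropout that depends on a score never recorded. It then projects the leaver's later course from similar patients who stayed, and those did better.

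In this study the change over time is the entire efficacy result. No control arm would reveal or offset a selective loss of worsening patients. Without reasons for leaving, the sponsor also could not show afterwards that the loss was harmless.

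**Working it through.** **1. Inputs from the plan (Section G).** n = 75-100; two-sided alpha 0.05; expected baseline 4-5 on the 0-10 patient scales; expected fall 2-3 points; SD by a rule of thumb from the scale range, with no number given.

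**2. Reproducing the plan's own figure.** Take SD = range/4, so 10/4 = 2.5 and 3/4 = 0.75. The detectable difference at 80% power is (1.960 + 0.842) × SD / √n.
- Patient scales: 2.802 × 2.5 / √75 = 0.81, and 2.802 × 2.5 / √100 = 0.70. The plan says 0.7-0.8.
- Physician scales: 2.802 × 0.75 / √75 = 0.24, and 2.802 × 0.75 / √100 = 0.21. The plan says 0.21-0.25.

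The plan's figures are reproduced with 2.5 as the SD of the before/after difference. A score SD of 2.5 with within-patient correlation 0.5 gives that same SD: 2.5 × √(2 × (1 - 0.5)) = 2.5. Both values are therefore used below.

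**3. Assumptions not in the documents.** Four visits, normal scores, baseline mean 4.5, no true change. A patient whose score has risen by more than 2 points leaves with a set probability, and the score at exit is or is not recorded. Under no change, the chance of such a rise from baseline at a given visit is 1 - Φ(2/2.5) = 1 - Φ(0.8) = 0.21. The estimate is the maximum-likelihood month-12 change with unstructured covariance.

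**4. Results, no true change.**

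| Patients with rise > 2 who leave | Exits scored | Total dropout | Month-12 bias | False-positive rate |
|---|---|---|---|---|
| 50% | none | 25-30% | -0.4 to -0.5 | about 26% (n=75), 37% (n=100) |
| 50% | half | about 25% | -0.20 | 10-12% |
| 20% | none | about 12% | -0.17 | 8-10% |
| 20% | half | about 12% | -0.07 | about 6% |
| 50% | all | about 25% | about 0 | about 5% |

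In the first row, the lower values (25%, -0.4) measure the rise from baseline and the upper values (30%, -0.5) from the previous visit.

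**5. How the false-positive rates arise.** Rate = Φ(-1.96 + b/s) + Φ(-1.96 - b/s), where b is the size of the bias and s the SD of the estimate.
- Top row, n = 75: b/s = 0.39/0.30 = 1.30, giving Φ(-0.66) + Φ(-3.26) = 0.26.
- Top row, n = 100: b/s = 0.43/0.26 = 1.65, giving about 0.38 from these rounded inputs. A direct count in a rerun gave 37%.
- Third row: 0.17/0.30 = 0.57 and 0.17/0.26 = 0.65, giving about 0.09 and 0.10.

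**6. Hand check.** Bias is roughly the fraction lost times the gap between the leavers' unrecorded scores and what the model projects for them. With a 2-point gap, 10% lost gives 0.2 and 20% lost gives 0.4.

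**7. If there is a true effect.** Under the top-row rule, with the rise measured from baseline, a true change of -1.0 is estimated as -1.28 and a true change of -2.5 as -2.66. The second excess is 0.16 points (0.16/2.5 = 6%). It is small because few patients then rise by more than 2 points.

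A deliberately harsher mechanism fixes total dropout at 12%, 20% or 30% and always removes the patients with the largest unrecorded rises. With a true change of -2.5 and correlation 0.5 it gives biases of -0.23, -0.42 and -0.63.

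**8. Contrast.** When the worsening is scored at one visit and the patient leaves before the next, the same model is within 0.02 points of the truth at each of those three dropout levels.

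**The case against.** A reader might infer three stronger things from these sections. The documents support none of them.

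- **That worsening patients will withdraw.** No section says so and no rate is given. Section 2.f names loss of interest, ineligibility and safety. Section B1 describes the available treatments as few and inconsistent, which weakens the incentive to leave for them. A worsening patient may also stay, or add therapy and stay, which is a different problem. If improving patients left equally often, the bias would be about zero.
- **That the worsening behind an exit usually goes unscored.** Section 2.g allows contact in person at an office visit, and F3 has the assessment form completed at every office visit. Such a patient can be scored first, and that score is then pre-withdrawal data. The clear gap is the exit by phone. If the abstract's monthly visits applied and were scored, less worsening could be missed.
- **That 2.h itself creates the bias.** It does not. Keeping all pre-withdrawal data in a likelihood model is right, and step 8 shows no material bias when the worsening has been scored.

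It is also fair to say that, at the 2-3 point effect the plan expects, a bias of about 0.16 would not change the conclusion.

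These arguments limit how certain and how large the bias is. They do not close the gap: the plan requires neither an exit score nor a reason for leaving, and neither can be recovered later.

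**Conclusion.** The point holds as a conditional one. If patients leave because of worsening that has not been scored, the month-12 time effect is biased towards benefit.

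Under no true change, SD 2.5 and correlation 0.5, the bias is about -0.2 points (20% of patients with a rise above 2 points leave unscored, or 50% leave and half of the exits are scored). It reaches about -0.4 to -0.5 if 50% leave and none is scored. Against the 0.7-0.8 points the plan is powered to detect, that is from a quarter (0.2/0.8) to about 70% (0.5/0.7). Milder assumptions give less, and scoring every exit brings it to about zero.

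It matters most if the true effect is small or absent. The dropout rate, the leaving rule and the share of exits scored are all assumptions. Confidence is moderate. The change is worth making because it is cheap and the data are otherwise lost.

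**What to change.** 1. **Exit data (2.h).** At the contact already planned in 2.g, record the reason for leaving and a dated exit score: itch and burning/pain by phone or in person, erythema and scale if the patient is seen.
2. **Later scores (2.h).** For patients who agree, keep recording the month 3, 6 and 12 scores at routine clinic visits, with the date of any added LPP/FFA therapy.
3. **Main analysis (G).** State the missing-data assumption and how scores after added therapy are handled. Include exit scores in the mixed model at their actual time. This needs a covariance structure defined by time, or a visit window fixed in advance.
4. **Sensitivity analysis (G).** Add one analysis that makes the later missing values of patients who left for worsening less favourable over a range of shifts, for example 1, 2 and 3 points on the 0-10 scales, and report the shift at which the conclusion changes.
5. **Schedule.** Reconcile the monthly, six-month schedule in A1 with the 0, 3, 6 and 12 month schedule in 3.e, F2 and G, since it determines how much worsening can go unscored.

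This changes data collection and analysis only. The treatment rule in 3.f is untouched. The cost is a short amendment and a few extra scores at contacts that already take place. Some leavers will not be reached, so the bias is reduced rather than removed, and the estimated benefit may come out slightly smaller.
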